4.2 METHOD OF TREATMENT ASSIGNMENT AND BLINDING

This is an open-label study. Dose assignments will be based on age.

4.3 STUDY TREATMENT

4.3.1 Formulation, Packaging, and Handling

Atezolizumab will be supplied by the Sponsor as sterile liquid in 20-mL glass vials. The vial is designed to deliver 20 mL (1200 mg) of atezolizumab solution but may contain more than the stated volume to enable delivery of the entire 20-mL volume.

For information on the *formulation* and handling of atezolizumab, see the Investigator's Brochure *and Pharmacy Manual*.

4.3.2 Dosage, Administration, and Compliance

The dose of atezolizumab is 15 mg/kg (maximum, 1200 mg) for patients aged <18 years. An interim analysis will be performed after 5 patients of <6 years of age have completed the first cycle. Dose adjustments may be made, if necessary, to achieve exposures corresponding to those measured in adult patients and if the safety profile is acceptable (see Section 5.1.1.1). Patients aged ≥ 18 years will receive a flat dose of 1200 mg of atezolizumab. Atezolizumab will be administered by IV infusion once every 3 weeks. Patients will be weighed at the beginning of each cycle (within 7 days of the Day 1 dose), and the dose will be adjusted as needed. Atezolizumab infusion may be delayed up to 5 days to accommodate holidays, weekends, and other patient obligations. Subsequent

infusions should be rescheduled accordingly. For patients who receive the 15-mg/kg dose, the dose administered should be within 5% of the calculated dose to accommodate for any rounding that may need to occur.

Administration of atezolizumab will be performed in a setting with emergency medical facilities and staff who are trained to monitor for and respond to medical emergencies. In addition, there must be at least 24 hours between the initial treatment doses of the first 5 patients regardless of tumor type to allow for evaluation of immediate immune activating events before additional patients are exposed to atezolizumab. There must also be at least 24 hours of treatment doses for the first 3 patients within each tumor type cohort.

Atezolizumab will be delivered in variable-size 0.9% NaCl IV infusion bags. The size of the infusion bag for each dose is listed below and will accommodate fluid restrictions needed for smaller patients.

Dose (mg)	Infusion Bag Size (mL)
600–1200	250
240–599	100
45–239	25

The initial dose of atezolizumab will be *administered* over 60 (± 15) minutes. If the first infusion is tolerated without infusion-associated adverse events, the second infusion may be delivered over 30 (± 10) minutes. If the 30-minute infusion is well tolerated, all subsequent infusions may be *administered* over 30 (± 10) minutes. For the first infusion, the patient's vital signs (heart rate, respiratory rate, blood pressure, temperature, and pulse oximetry) should be determined within 60 minutes before, during (every 15 [± 5] minutes), and 30 (± 10) minutes after the end of infusion. For subsequent infusions, vital signs will be collected within 60 minutes before infusion and at the end of the infusion (± 10 minutes). Patients or their caregivers will be informed about the possibility of delayed post-infusion symptoms and instructed to contact their study physician if they develop such symptoms.

No premedication will be allowed for the first dose of atezolizumab. Premedication, including acetaminophen, diphenhydramine, or other standard-of-care medications, may be administered for Cycles ≥ 2 at the discretion of the treating physician after consultation with the Medical Monitor. Corticosteroids cannot be administered as premedication. Patients who are receiving acetaminophen, diphenhydramine, or other medications for symptom management may continue to receive their scheduled medications without interruption.

Guidelines for dosage modification and treatment interruption and for the management of specific adverse events, including infusion-related reactions, are provided in Section 5.1.1.

Any overdose or incorrect administration of study drug should be noted on the Study Drug Administration electronic Case Report Form (eCRF). Adverse events associated with an overdose or incorrect administration of study drug should be recorded on the Adverse Event eCRF.

For more detailed information on drug preparation, storage, and administration, refer to the Investigator's Brochure and Pharmacy Manual.

4.3.3 Investigational Medicinal Product Accountability

All investigational medicinal product (IMP) required for completion of this study (i.e., atezolizumab) will be provided by the Sponsor where required by local health authority regulations. The study site will acknowledge receipt of IMP, using the IxRS to confirm the shipment condition and content. Any damaged shipments will be replaced.

IMP will either be disposed of at the study site according to the study site's institutional standard operating procedure or returned to the Sponsor with the appropriate documentation. The site's method of IMP destruction must be agreed to by the Sponsor. The site must obtain written authorization from the Sponsor before any IMP is destroyed, and IMP destruction must be documented on the appropriate form.

Accurate records of all IMP received at, dispensed from, returned to, and disposed of by the study site should be recorded on the drug accountability log and IxRS.

4.3.4 Post-Study Access to Atezolizumab

The Sponsor will offer post-study access to the study drug (atezolizumab) free of charge to eligible patients in accordance with the Roche Global Policy on Continued Access to Investigational Medicinal Product, as outlined below.

A patient will be eligible to receive study drug after the end of the study if all of the following conditions are met:

- The patient has a life-threatening or severe medical condition and requires continued study drug treatment for his or her well-being
- There are no appropriate alternative treatments available to the patient
- The patient and his or her doctor comply with and satisfy any legal or regulatory requirements that apply to them

A patient will not be eligible to receive study drug after the end of the study if any of the following conditions are met:

- The study drug is commercially marketed in the patient's country and is reasonably accessible to the patient (e.g., is covered by the patient's insurance or wouldn't otherwise create a financial hardship for the patient)
- The Sponsor has discontinued development of the study drug or data suggest that the study drug is not effective for solid tumors
- The Sponsor has reasonable safety concerns regarding the study drug as treatment for solid tumors
- Provision of study drug is not permitted under the laws and regulations of the patient's country

The Roche Global Policy on Continued Access to Investigational Medicinal Product is available at the following Web site:

http://www.roche.com/policy_continued_access_to_investigational_medicines.pdf

4.4 CONCOMITANT THERAPY AND FOOD

4.4.1 Permitted Therapy

Concomitant therapy includes any medication (e.g., prescription drugs, over-the-counter drugs, herbal or homeopathic remedies, nutritional supplements) used by a patient from 7 days prior to study drug initiation to the study drug discontinuation visit. All such medications should be reported to the investigator and recorded on the Concomitant Medications eCRF.

Patients who use oral contraceptives, hormone-replacement therapy, prophylactic anticoagulation therapy, or maintenance therapies other than prohibited therapies listed in Section 4.4.2 should continue their use, including stress dosing as clinically indicated.

Pain medications may be administered according to local standard practice guidelines while the patient is in the study.

Patients who experience infusion-associated symptoms should receive supportive care with oxygen, β -agonists, antihistamines, antipyretics, or corticosteroids, as considered appropriate by the investigator (see the Atezolizumab Investigator's Brochure, Section 5.1.1, and Appendix 10 for more information).

Systemic corticosteroids may attenuate potential beneficial immunologic effects of treatment with atezolizumab; however, they may be administered, as described in Section 5.1.1.2, after consultation with the Medical Monitor. If feasible, alternatives to corticosteroids should be considered. Premedication, excluding corticosteroids, may be administered for Cycles ≥ 2 at the discretion of the treating physician after consultation with the Medical Monitor.

Palliative radiotherapy may be given to patients (e.g., treatment of known bone metastases) provided it does not interfere with assessment of tumor target lesions. It is not required to withhold atezolizumab during palliative radiotherapy.

Patients may receive inactivated vaccines if deemed necessary by the treating physician. Influenza vaccination can be given during influenza season (approximately October to March in the Northern Hemisphere). Acceptable influenza vaccines include TIV and QIV (injection of trivalent or quadrivalent killed vaccine). However, LAIV and Q/LAIV (nasal spray of live attenuated influenza vaccine such as FluMist®) must be avoided.

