4.4.2 Prohibited Therapy

Use of the following therapies is prohibited during the study:

- Any concomitant therapy intended for the treatment of solid tumors, either approved by health authorities or experimental, including chemotherapy, radiotherapy (except palliative radiotherapy), hormonal therapy, immunotherapy, biologic therapy, or herbal therapy

Patients with rhabdoid tumor and ATRT may receive local therapy (radiation or surgery) after at least four cycles of atezolizumab with approval of the Medical Monitor.
- Traditional herbal or homeopathic or natural medicines

Ingredients for such medicines have not been fully studied, and their use may result in unanticipated drug-drug interactions that may cause or confound assessment of toxicity.
- Immunostimulatory agents, including but not limited to interferon (IFN)- α , IFN- γ , anti-TNF- α , or IL-2 (prohibited during the study and for 10 weeks after the last dose of atezolizumab)

These agents, in combination with atezolizumab, could potentially increase the risk for autoimmune conditions.
- Immunosuppressive medications, including but not limited to cyclophosphamide, azathioprine, methotrexate, and thalidomide

These agents could potentially alter the activity and the safety of atezolizumab.
- Live vaccines and live attenuated vaccines (prohibited during the study and for 5 months after the last dose of study drug)

Initiation of granulocyte colony-stimulating factors (e.g., granulocyte colony-stimulating factor, granulocyte/macrophage colony-stimulating factor, and/or pegfilgrastim) should be discussed with the Medical Monitor.

Systemic corticosteroids may attenuate potential beneficial immunologic effects of treatment with atezolizumab but may be administered at the discretion of the treating physician after consultation with the Medical Monitor, as described in Section 5.1.1.2.

Patients with ATRT can be receiving concurrent treatment with corticosteroids with approval from the Medical Monitor. Patients must be receiving a stable or decreasing dose for ≥ 5 days prior to the baseline MRI scan and at the time of drug initiation. The Medical Monitor should be informed when steroid doses are increased because of declining patient status.

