6.6.1 Primary Efficacy Endpoint

The primary endpoints for efficacy are ORR and PFS. For patients with measurable disease or patients with neuroblastoma who have evaluable disease at baseline, an objective response is defined as a complete or partial response on two consecutive occasions ≥ 4 weeks apart, as determined by the investigator using RECIST v1.1 for patients with solid tumors (see [Appendix 6](#)), *mINRC* for patients with neuroblastoma (see [Appendix 3](#)), Revised Response Criteria for Malignant Lymphoma for patients with Hodgkin's lymphoma or non-Hodgkin's lymphoma (see [Appendix 4](#)), and *RANO criteria* (see [Appendix 11](#)) for patients with ATRT.

For patients with non-measurable but evaluable disease at baseline (except *patients with neuroblastoma*), an objective response is defined as a complete response on two consecutive occasions ≥ 4 weeks apart, as determined by the investigator using RECIST v1.1 for patients with solid tumors (see [Appendix 6](#)), Revised Response Criteria for Malignant Lymphoma for patients with Hodgkin's lymphoma or non-Hodgkin's lymphoma (see [Appendix 4](#)), and *RANO criteria* (see [Appendix 11](#)) for patients with ATRT.

ORR is the percentage of patients who are determined to have an objective response. Patients with no post-baseline tumor assessments will be counted as non-responders. ORR and corresponding 95% exact CI using the Blyth–Still–Casella method will be summarized overall and by tumor type cohort (except for the osteosarcoma tumor type cohort).

CBR is defined as objective response or stable disease for at least 6 months, as determined by RECIST v1.1 for patients with osteosarcoma (see [Appendix 6](#)). CBRR is the percentage of patients who are determined to have a CBR. Patients with no post-baseline tumor assessments will be counted as not having CBR. CBRR and corresponding 95% CI will be summarized for the osteosarcoma tumor type cohort only.

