Appendix 2 Schedule of Pharmacokinetic, Pharmacodynamic, and Immunogenicity Assessments

Visit	Timepoint	Sample Type
Cycle 1, Day 1	Prior to the infusion	Serum for atezolizumab PK and ATA ^a EDTA plasma and whole blood for PD
	30 (± 10) min after the end of the infusion	Serum for atezolizumab PK
Cycle 1, Day 8	Any time during visit	Serum for atezolizumab PK
Cycle 2, Day 1	Prior to the infusion ^b	Serum for atezolizumab PK and ATA ^a Plasma and whole blood for PD
Cycle 3, Day 1	Prior to the infusion ^b	Serum for atezolizumab PK and ATA ^a Plasma and whole blood for PD
Cycle 4, Day 1	Prior to the infusion ^b	Serum for atezolizumab PK and ATA ^a
	30 (± 10) min after the end of the infusion	Serum for atezolizumab PK
Cycle 8, Day 1	Prior to the infusion ^b	Serum for atezolizumab PK and ATA ^a Plasma and whole blood for PD
Cycle 12, Day 1	Prior to the infusion ^b	Serum for atezolizumab PK and ATA ^a Plasma and whole blood for PD
Day 1 of Cycle 16 and every 8 cycles thereafter	Prior to the infusion ^b	Serum for atezolizumab PK and ATA ^a Plasma and whole blood for PD
Study drug discontinuation visit	Any time during visit	Serum for atezolizumab PK and ATA ^a Plasma and whole blood for PD
At least 90 days (but no more than 150 days) after last dose of study drug	Any time during visit	Serum for atezolizumab PK and ATA ^a Plasma and whole blood for PD

ATA=anti-therapeutic antibody; PD=pharmacodynamic; PK=pharmacokinetic.

^a Serum samples will be split into 2 × 500 µL serum aliquots, one for PK and one for ATA.

^b Blood draws can occur up to 2 days prior to infusion.

Appendix 3

Modified International Neuroblastoma Response Criteria

Below response assessment is modified from the original INRC publication in 1993.

DEFINITION OF MEASURABLE (EVALUABLE) DISEASE ON CT/MRI SCAN

The presence of at least one lesion that can be accurately measured in at least one dimension with the longest diameter at least 20 mm. With a spiral CT scan, lesions must be at least 10 mm. The investigator will identify up to 10 measurable target lesions to be followed for response. Note that bone lesions will be considered as non-target lesions for evaluation of CT/MRI response since they will be evaluated with MIBG scans.

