Patient may be declared to have PD in bone marrow after only one diagnostic bone marrow at the discretion of the treating physician
Patients who enter study with bone marrow tumor by morphology will be considered to have PD if there is a minimum of 25% tumor in the marrow by morphology and a doubling in the amount of tumor in the marrow compared with the level present at study entry. For example, a patient entering with 5% tumor in marrow by morphology must increase to >25% tumor to have PD; a patient entering with 30% tumor must increase to >60% tumor.
- SD: Persistence of an amount of tumor in the bone marrow by morphology that does not meet criteria for either CR or PD
Patients who clear morphologic tumor but have immunocytologic tumor will be called SD.

RESPONSE CRITERIA FOR MIBG-POSITIVE LESIONS

All patients with known MIBG-avid lesions will be evaluable for MIBG response following the first course of therapy. The following criteria will be used to report MIBG response:

- CR: Complete resolution of all MIBG-positive lesions
- PR: Resolution of at least one MIBG-positive lesion, with persistence of other MIBG positive lesions
- SD: No change in MIBG scan in number of positive lesions (includes patients who have same number of positive lesions but decreased intensity)
- PD: Development of new MIBG-positive lesions

Appendix 3

International Neuroblastoma Response Criteria (cont.)

DEFINITION OF OVERALL RESPONSE FOR EACH PATIENT WITH NEUROBLASTOMA

The International Neuroblastoma Response Criteria were developed to define responses in patients being treated with frontline therapy from diagnosis.¹ These criteria were utilized as a basis for the following response criteria, which integrate response at all sites defined as measurable in this study, including CT/MRI lesions that meet RECIST criteria, MIBG-positive lesions, and bone marrow disease. These criteria will be used to define the overall response for each patient.

- CR: Disappearance of all target lesions; no evidence of tumor at any site (chest, abdomen, liver, bone, bone marrow, nodes, etc.); homovanillic acid (HVA) and vanillylmandelic acid (VMA) normal

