A lesion identified during the study in an anatomical location that was not scanned at baseline is considered a new lesion and will indicate disease progression.

If a new lesion is equivocal, for example because of its small size, continued therapy and follow-up evaluation will clarify if it represents truly new disease. If repeat scans confirm there is definitely a new lesion, then progression should be declared using the date of the initial scan.

EVALUATION OF RESPONSE

a. Timepoint Response (Overall Response)

It is assumed that at each protocol-specified timepoint, a response assessment occurs. [Table 1](#) provides a summary of the overall response status calculation at each timepoint for patients who have measurable disease at baseline.

When patients have non-measurable (therefore, non-target) disease only, [Table 2](#) is to be used.

Appendix 6 Response Evaluation Criteria in Solid Tumors: Modified Excerpt from Original Publication (cont.)

**Table 1 Timepoint Response: Patients with Target Lesions
(with or without Non-Target Lesions)**

Target Lesions	Non-Target Lesions	New Lesions	Overall Response
CR	CR	No	CR
CR	Non-CR/non-PD	No	PR
CR	Not evaluated	No	PR
PR	Non-PD or not all evaluated	No	PR
SD	Non-PD or not all evaluated	No	SD
Not all evaluated	Non-PD	No	NE
PD	Any	Yes or no	PD
Any	PD	Yes or no	PD
Any	Any	Yes	PD

CR=complete response; NE=not evaluable; PD=progressive disease;
PR=partial response; SD=stable disease.

**Table 2 Timepoint Response: Patients with Non-Target
Lesions Only**

Non-Target Lesions	New Lesions	Overall Response
CR	No	CR
Non-CR/non-PD	No	Non-CR/non-PD ^a
Not all evaluated	No	NE
Unequivocal PD	Yes or no	PD
Any	Yes	PD

CR=complete response; NE=not evaluable; PD=progressive disease.

^a “Non-CR/non-PD” is preferred over “stable disease” for non-target disease since stable disease is increasingly used as an endpoint for assessment of efficacy in some studies; thus, assigning “stable disease” when no lesions can be measured is not advised.

b. Missing Assessments and Not-Evaluable Designation

When no imaging/measurement is done at all at a particular timepoint, the patient is not evaluable at that timepoint. If only a subset of lesion measurements are made at an assessment, usually the case is also considered not evaluable at that timepoint, unless a

Appendix 6

Response Evaluation Criteria in Solid Tumors: Modified Excerpt from Original Publication (cont.)

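### No rule says how to score a non-target or MIBG-positive lesion irradiated on study, so palliative radiotherapy can complete a response that counts in ORR

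*Combined protocol and SAP*

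**What the plan says.** **The permission.** Section 4.4.1 states: "Palliative radiotherapy may be given to patients (e.g., treatment of known bone metastases) provided it does not interfere with assessment of tumor target lesions". It adds: "It is not required to withhold atezolizumab during palliative radiotherapy". Section 4.4.2 exempts palliative radiotherapy from its list of prohibited treatments. Neither section limits this to particular cohorts. The separate 4.4.2 allowance of local therapy for rhabdoid tumor and ATRT is not at issue here.

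**Neuroblastoma scoring.** Appendix 3 says that "bone lesions will be considered as non-target lesions for evaluation of CT/MRI response since they will be evaluated with MIBG scans". Its MIBG definition of partial response is "Resolution of at least one MIBG-positive lesion, with persistence of other MIBG positive lesions". Overall PR needs a CT/MRI decrease of at least 30%, marrow CR, and MIBG PR or CR in bone lesions.

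**Non-measurable disease under RECIST.** Appendix 6 sends these patients to its Table 2 ("When patients have non-measurable (therefore, non-target) disease only"), which uses non-target lesions alone. For such patients, apart from those with neuroblastoma, Section 6.6.1 says "an objective response is defined as a complete response on two consecutive occasions", at least 4 weeks apart.

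**Existing text on irradiated lesions.** Appendices 5 and 6 bar lesions irradiated in the 3 weeks before Cycle 1 Day 1 from being targets, and say that previously irradiated lesions are usually not measurable unless they have progressed. Appendix 4 lists irradiated lesions among examples of non-target lesions. All of this classifies lesions at baseline. For ORR, Section 6.6.1 handles only patients with no post-baseline tumor assessment.

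**The concern.** The only endpoint safeguard in 4.4.1 refers to target lesions, and its own example of radiotherapy is bone metastases. In neuroblastoma those lesions are never CT/MRI targets, yet they decide the MIBG component. In non-measurable disease there is no target lesion at all, so the safeguard has nothing to act on. In both settings, radiotherapy given in full compliance with the protocol can change the response category, and the plan does not say that the change should be disregarded.

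A radiation effect could then be credited to atezolizumab in the primary ORR and in the Table 3 responder count. The study has a single arm and reads both against historical rates, so no control group would absorb the effect.

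**Working it through.** **Step 1. Tracing the rules**

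| Case | Before radiation | Change after radiation | Result as written |
|---|---|---|---|
| Neuroblastoma (Appendix 3, Table 1) | CT/MRI PR, marrow CR, MIBG SD: overall SD | One irradiated bone lesion resolves, others persist: MIBG PR | Overall PR; counts under 6.6.1 if confirmed |
| RECIST, non-measurable disease only (Appendix 6, Table 2) | Sole or last lesion persists: non-CR/non-PD | That lesion disappears: non-target CR (markers normal, if applicable) | Overall CR; counts under 6.6.1 if confirmed |

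In neither case does the target-lesion condition in 4.4.1 come into play.

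A third case cannot be resolved from the text. For neuroblastoma with MIBG-positive disease only, 6.6.1 counts PR as well as CR. Section 4.5.5.2 says that PR cannot be determined in evaluable-only disease and makes no neuroblastoma exception. Appendix 3, Table 1 has no row for a patient without CT/MRI lesions.

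**Step 2. Inputs for size**

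Table 3 gives neuroblastoma a historical ORR of 18%, 10 patients and a minimum of 3 responders. Several other cohorts have 10%, 10 patients and a minimum of 2. The plan attaches no error rate to these rules and states that no formal hypothesis testing is planned, so there is no operating figure of its own to reproduce. The documents give no rate of on-study palliative radiotherapy. The number of responders who depend on radiation is therefore an assumption, shown from 0 to 2.

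**Step 3. Exact binomial probabilities**

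Let s be the number of patients among the 10 who respond only because of radiation. The other 10 − s respond at the historical rate p. The chance of meeting a minimum of r is P(X ≥ r − s), with X binomial(10 − s, p).

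Neuroblastoma (p = 0.18, r = 3):
- s = 0: 1 − 0.82^10 − 10 × 0.18 × 0.82^9 − 45 × 0.18² × 0.82^8 = 0.263
- s = 1: 1 − 0.82^9 − 9 × 0.18 × 0.82^8 = 0.501
- s = 2: 1 − 0.82^8 = 0.796

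A 10% cohort (p = 0.10, r = 2):
- s = 0: 1 − 0.90^10 − 10 × 0.10 × 0.90^9 = 0.264
- s = 1: 1 − 0.90^9 = 0.613

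The rows with s of 1 or 2 are conditional on such patients being present. If instead radiation is assumed to add 1 percentage point to each neuroblastoma patient's response probability (18% to 19%), P(X ≥ 3) with n = 10 is 0.29 against 0.26. If it adds 5 points (23%), the figure is 0.41.

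**The case against.** The strongest case against the point is that the path is narrow and the consequence limited. Much of this stands.

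- **Neuroblastoma.** A reader might infer that irradiating one bone lesion by itself produces an objective response. For a patient with CT/MRI lesions, the documents do not support that: CT/MRI PR and marrow CR must be present as well, and the response must be confirmed. Radiation can only supply the missing MIBG component.
- **Non-measurable disease.** Outside neuroblastoma only confirmed CR counts, so the irradiated lesion must be the sole or last one. It is also arguable whether irradiating a patient's only site is palliative or falls under the 4.4.2 prohibition. Appendix 11 caps ATRT with non-measurable disease only at stable disease (although 6.6.1 would allow CR), and the osteosarcoma cohort is summarised by clinical benefit response rather than ORR.
- **Expansion.** It would be too strong to say that the responder count alone decides expansion. Sections 3.1 and 6.1 also weigh feasibility, biomarkers, safety and other information, and Section 6.8.2 describes the study as hypothesis-generating.
- **Size.** Nothing in the documents anchors a gain of 5 or 10 percentage points. At 1 point the effect on the neuroblastoma rule is small.

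These points limit how often the problem can arise. They do not supply a rule for when it does: no text in 6.6.1 or the appendices tells the investigator or the analyst how to score the irradiated lesion.

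**Conclusion.** The point holds as a gap in the scoring rules. As written, they can count a response whose deciding component is a lesion irradiated on study, in neuroblastoma through the MIBG component and in RECIST non-measurable disease through a sole or last lesion. Frequency is unknown and probably low, given how many conditions must coincide.

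One such patient would still matter. At the historical 18%, the chance that neuroblastoma meets its minimum goes from 0.26 with no radiation-dependent responder to 0.50 with one. That figure assumes one such responder and the historical rate in the other nine; it does not estimate the bias to be expected.

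A reader might go further and conclude that the 4.4.1 permission is itself wrong and should be narrowed. The documents do not support that. The permission is a clinical matter, and the defect lies in how responses are scored afterwards.

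**What to change.** Leave 4.4.1 unchanged and add a scoring rule to Section 6.6.1 and Appendices 3 and 6:

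- For response, a lesion irradiated on study is scored as persisting unchanged from the date of radiation. Under MIBG this means not resolved; for a RECIST non-target lesion it means non-CR/non-PD.
- Its resolution therefore cannot supply MIBG PR or CR, or overall CR. Resolution of an unirradiated MIBG lesion still can supply MIBG PR, and a PR in unirradiated target lesions is kept.
- Progression still counts.

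Scoring the lesion as persisting works better than calling it not evaluable. Appendix 3, Table 1 has no not-evaluable row. Appendix 6 is inconsistent on the point: its Table 1 keeps a target PR when non-target lesions are not all evaluated, while its text on missing assessments makes the overall response unassessable.

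Record the site and date of on-study radiotherapy on the eCRF. Section 4.4.1 defines concomitant therapy as medication, and the schedule in Appendix 1 lists only concomitant medications, so this capture cannot be assumed to exist. Report ORR with and without the rule as a sensitivity analysis.

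Separately, reconcile 4.5.5.2 with 6.6.1 on whether PR can be assigned in evaluable-only neuroblastoma.

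The cost is one added data field and a few sentences. A few patients may lose a PR or CR, so ORR may be slightly lower.
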